4.6 Considerations for statistical analysis resulting from the COVID-19 PHE

4.6.1 Co-Primary Endpoints

Since the co-primary efficacy variable CSNS is based on electronic diaries used by subjects during this study, as described in Section 9.3.1, there is no anticipated impact of COVID-19 on the subject's ability to complete the diaries per the protocol. Therefore, there is no anticipated impact of COVID-19 on this co-primary endpoint.

For the co-primary endpoint APOV, the endpoint CT scan will occur at the Week 24 visit, or the ET visit if the subjects discontinues the study prior to Week 24. Since subjects must visit the clinic for the CT scan, subjects may be impacted by COVID-19 in a manner similar to other acute illnesses as described in the Protocol, Amendment 6, Section 6. In this circumstance a subject must be symptom-free for at least 28 days prior to undergoing the Week 24/ET CT scan, and consequently the Week 24/ET visit may be delayed. Subjects are instructed to continue on treatment until the EOS CT scan can be completed. There is no anticipated impact of such a delay on the APOV co-primary endpoint.

Thus, there is no practical impact of the COVID-19 PHE on either of the co-primary endpoints.

4.6.2 Secondary Endpoints

The following secondary efficacy variables are PROs which are self-administered by subjects during study visits:

- Sinonasal Outcome Test (SNOT-22) – a subject-completed questionnaire that consists of 22 symptoms and social emotional consequences of their nasal disorder.
- EuroQol-5 (EQ-5D) – a subject-completed 2-page questionnaire including the EQ-5D descriptive system and the EQ Visual Analogue Scale (EQ VAS).
- 36-Item Short Form Health Survey Version 2 (SF-36v2) – a subject-completed, multipurpose, 36-item subject-completed validated questionnaire that measures 8 domains of health.
- Short Form-6 Dimension (SF-6D) – a subject-completed single health state index derived from the 8 domains from the SF-36v2.
- Pittsburgh Sleep Quality Index (PSQI) – a self-rated, validated questionnaire, which assesses sleep quality and disturbances over a 1-month time interval.
- Quick Inventory of Depressive Symptomatology (QIDS) – a subject-completed 16-item questionnaire to assess the severity of depressive symptoms.

- Health and Work Performance Questionnaire (HPQ) – a subject-completed Health economic information questionnaire.
- Smell Identification Test (SIT) – a subject-completed test comprised of 4 booklets each containing 10 microencapsulated (scratch and sniff) odors.
- Patient Global Impression of Change (PGIC) – a subject-completed global impression of change scale assessment questionnaire.

4.6.2.1 Remote Study Visits

A COVID-19 Supplemental Guidance Document for Protocol CS-3205 has been provided to Investigators which includes detailed instructions for handling the PROs where remote visits are necessary.

For any subjects participating in study visits remotely, all PROs required for the visit will be sent by email to the subject or by courier directly to the subject's home for completion prior to the study visit. Site staff are instructed to notify study subjects to complete the self-administered PROs within two days prior to the remote study visit. At the time of this remote visit, the site staff are instructed to collect and document the information provided in the PROs in the patient's chart. Subject-completed hard copies of all PROs will be collected at the subject's next in-person visit or sent to the site by courier.

As subjects will complete the PROs before the virtual study visit, it will prevent the risk of study staff influencing subject responses. The site staff will verify the PROs were completed by the subjects at the virtual visit and the subjects will share their completed PRO responses. The subject's responses will be documented in the subject's chart.

Site staff are instructed to review the PRO responses provided during the virtual study visit with the hard copies of the PROs submitted by the subject after their visit. If any discrepancies are noted, site staff are instructed to update the Electronic Data Capture (EDC) system with the data from the hard copy. The hard copy subject-completed PROs are considered the source record and data from these will be reported in the EDC. Additionally, the study Monitoring Plan will include a requirement for monitors to confirm discrepant data during monitoring visits.

4.6.2.2 Sensitivity Analyses

The number and percentage of virtual visits will be summarized by study visit, overall and by treatment group, in order to assess the extent of the virtual visits in the study. Also, a tabulated listing of discrepancies between verbal responses reported at the virtual visit and reported on the PRO hard copies will be provided for each PRO.

A sensitivity analysis of the impact of virtual clinic visits will depend on the extent of the virtual visits at Baseline and Week 24/ET. If there are not sufficient virtual visits to include a term in the statistical model, then a statistical analysis excluding subjects with a virtual visit at Week 24/ET will be performed. The treatment difference and 95% confidence interval will be reported to assess consistency with the pre-specified analysis result.

If there are a sufficient number of virtual visits to include in a statistical model then a categorical variable for visit type (in-clinic, virtual) and treatment-by-visit type interaction will be included in the statistical model. The treatment difference and 95% confidence interval in each subgroup will be reported to assess consistency with the pre-specified analysis result.

It is assumed that both the number and percentage of data discrepancies between the verbal report and the hard copy report will be small. A statistical analysis excluding subjects with discrepant results at Week 24/ET will be performed. The treatment difference and 95% confidence interval will be reported to assess consistency with the pre-specified analysis result.

Modification of these analyses or other sensitivity analyses of secondary endpoints may be considered, as appropriate, once the extent of the virtual visits is determined.

5 ANALYSIS POPULATION SETS

5.1 Enrolled Subjects

This set will include all subjects screened and who have signed the informed consent.

5.2 Single-Blind Run-In Set

The single-blind run-in set includes all subjects who received at least one dose of placebo EDS in the placebo run-in period.

5.3 Intent-to-treat (ITT) Analysis Set

The ITT analysis set will include all subjects who are randomized regardless of whether they received double-blind treatment.

5.4 Safety Analyses Set

The safety analysis set will include all randomized subjects who receive at least one dose of randomized study drug. The treatment group assignment in this population will be defined by the treatment actually received. The safety population will be used for the analysis of safety.

5.5 Full Analysis Set (FAS)

The FAS will include all subjects in the ITT set who receive at least one dose of randomized study treatment during the double-blinded treatment phase and have a baseline efficacy measurement for APOV endpoint, and also have a baseline value and at least one post-baseline value (7-day average AM instantaneous CSNS score) on or before Week 4 (i.e., Week 2 and/or Week 4) for the CSNS endpoint. Subjects will be included in the treatment group to which they were randomized.

The FAS population will be the primary study population for all efficacy analyses in this study.

5.6 Per Protocol Analysis Set (PPS)

The PPS analysis set excludes subjects from the FAS population due to major protocol deviations with potential to substantively affect the results of the primary efficacy analysis. The PPS population will be used for a sensitivity analysis for primary and key secondary efficacy endpoints.

Determination of the major protocol deviations will be made prior to unblinding of the database and documented in a separate report. Examples may include but are not necessarily limited to:

- Subjects who did not use study medication for more than 15 consecutive days in a given month
- Subjects who used a prohibited medication (e.g., oral steroids)
- Subjects who have sinus surgery during the study
- Subjects with an acute sinus exacerbation, for example as evidenced by taking antibiotics for sinus infection, within 28 days of a study-directed CT scan (screening or Week 24/ET)

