#### **9.3.1 Co-primary Endpoints**

- Change from baseline to the end of Week 4 in 7-day average instantaneous AM CSNS (evaluation of symptom severity immediately preceding the time of scoring):
  - nasal congestion
  - nasal discharge (anterior and/or posterior)
  - facial pain or pressure sensation

The baseline CSNS will be the average of the CSNS over the last 7 days of the placebo run-in period prior to randomization. The CSNS at Week 4 will be the average of the CSNS over the 7 days prior to nominal Study Day 28.

AND

- Change from baseline to Week 24/ET in the APOV in the ethmoid and maxillary sinuses (APOV is the average percentage of volume opacified across both maxillary and ethmoid sinuses (all 4 sinuses) at each time point)

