7.7 Per Protocol Analysis

As a sensitivity analysis, the co-primary endpoints will be analyzed using the Per Protocol Set, defined in Section 5.6, according to the primary estimand and estimation methods used in the primary analyses and described in Sections 7.1.1–7.1.5.

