9 DATA HANDLING RULES AND DEFINITIONS

9.1 Data Handling Conventions

9.1.1 Study Days and Duration

Study Day 1 is the date of first dose of randomized treatment with study drug after randomization; it is typically the date of randomization.

Study days will be numbered relative to the first day of randomized study drug administration.

- Study days will be numbered relative to study start (i.e., ..., -2, -1, 1, 2, ...; with **Day 1** being the start of study drug and **Day -1** being the day before the start of study drug).
- The elapsed time since Day 1 for an event (e.g. onset of an adverse event) will be calculated as [date of event – date of Day 1 + 1].
- For the purpose of converting days to years or months, one year = 365.25 days, and one month = 30.44 days.

Study Duration is defined as follows:

$$\begin{aligned} & (\text{Date of Double Blind Treatment completion or discontinuation} \\ & \quad - \text{Date of First Day of Study Drug}) + 1 \end{aligned}$$

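### One per-protocol set serves a co-primary finished on Day 27 and one measured at Week 24/ET, so later events remove subjects from the Week 4 CSNS per-protocol analysis

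*SAP*

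**What the plan says.** SAP 5.6 (and Protocol 9.2.4) builds the PPS by removing subjects from the FAS for major deviations that could substantively affect the primary efficacy analysis. These are decided before unblinding and recorded in a separate report. SAP 5.6 gives four examples and says that the list is not exhaustive:

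- non-use of drug: "Subjects who did not use study medication for more than 15 consecutive days in a given month";
- any use of a prohibited medication, with oral steroids as the instance;
- sinus surgery at any time in the study;
- an acute sinus exacerbation, for instance one shown by antibiotic use, close to either the screening or the Week 24/ET CT (a 28-day rule).

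On its use, SAP 5.6 states: "The PPS population will be used for a sensitivity analysis for primary and key secondary efficacy endpoints". SAP 7.7 is narrower: "As a sensitivity analysis, the co-primary endpoints will be analyzed using the Per Protocol Set, defined in Section 5.6". It does not mention the key secondaries. Neither section gives a cut-off date or a separate set by endpoint.

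The two co-primaries are measured at different times. Protocol 9.3.1 states: "The CSNS at Week 4 will be the average of the CSNS over the 7 days prior to nominal Study Day 28". SAP Table 9.1 makes that Days 21 to 27. APOV is the change to the Week 24/ET CT, nominally Day 168.

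**The concern.** A per-protocol analysis is meant to show the treatment effect among subjects who followed the protocol up to the time the endpoint was measured. A Week 4 score cannot be altered by an oral steroid course, an operation or an exacerbation in month 4 or 5. Removing the subject for such an event discards a valid score and makes membership of the CSNS set depend on what happened after the endpoint.

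The later events are also unlikely to be unrelated to treatment. The trial tests whether active drug lowers exacerbation frequency, and exacerbations lead to steroid use. If it does, more placebo than active subjects would leave the set. A difference between the PPS and FAS results for CSNS could then reflect selection after Day 27 rather than anything about adherence.

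The mismatch between 5.6 and 7.7 adds a second problem. If 5.6 is followed, exacerbation frequency is analysed after removing subjects partly because they had, or were treated for, an exacerbation.

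**Working it through.** **1. The plan's own figures.** SAP 4.2 gives 111 per group, two-sided 5%, and 88% power for a CSNS difference of 0.8 (SD 1.9) and for an APOV difference of 11.3 (SD 27). Using power = Φ(δ / (σ√(2/n)) − 1.96):

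- CSNS: 1.9 × √(2/111) = 0.255; 0.8/0.255 = 3.137; Φ(1.177) = 0.880.
- APOV: 27 × √(2/111) = 3.624; 11.3/3.624 = 3.118; Φ(1.158) = 0.877.

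Both agree with the stated 88%.

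**2. Dates.** The Week 4 score closes on Day 27. Days 28 to 168 are 141 of 168 treatment days (84%).

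| Listed exclusion | When it can occur | Can it change a Days 21–27 score? |
|---|---|---|
| Prohibited medication | Any time; Protocol 5.6.3 runs the systemic-steroid ban to study completion | Only if on or before Day 27 |
| Sinus surgery | Any time in the study | Only if on or before Day 27 |
| Non-use of drug | Any month | Only if it began by Day 27 |
| Exacerbation before the Week 24 CT | CT on Day 161, 168 or 175 (±7 days): look-back starts on Day 133, 140 or 147 | No |
| Exacerbation near an ET CT | Look-back reaches Day 27 if the CT is on or before Day 55 (55 − 28 = 27) | Possibly |
| Exacerbation near the screening CT | Can overlap the baseline window (Days −7 to −1) and the early treatment weeks | Yes, or the baseline score |

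**3. The same event in the primary analysis.** SAP 9.3.1 assigns the worst diary score only from the day of the intercurrent event onward. A CRS steroid course in month 4 therefore leaves the Week 4 CSNS untouched in the FAS analysis, while SAP 5.6 and 7.7 delete the subject from the CSNS per-protocol analysis. The plan gives no reason for the difference.

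**4. Loss of precision.** The documents give no PPS exclusion rate, so the following is an assumed range of removal for events after Day 27, equal in each arm:

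| Removed per arm | n per arm | CSNS power (0.8, SD 1.9) |
|---|---|---|
| 0% | 111 | 88% |
| 5% | 105 | 86% |
| 10% | 100 | 85% |
| 20% | 89 | 80% |
| 30% | 78 | 75% |

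Power serves here only as a yardstick, since the PPS analysis is not a confirmatory test.

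**5. Possible bias.** If a fraction p of an arm is removed and removal has correlation r with the Week 4 change, the mean of those retained shifts by −r × SD × √(p/(1−p)). Assume, purely for illustration, p = 0.20 on placebo and 0.10 on active:

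- r = 0.2: placebo −0.2 × 1.9 × 0.500 = −0.190; active −0.2 × 1.9 × 0.333 = −0.127. A true −0.80 becomes −0.80 − 0.127 + 0.190 = −0.737.
- r = 0.3: the shifts are −0.285 and −0.190, giving −0.705.

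That is 8% to 12% attenuation. The SE ratio is √((1/0.8 + 1/0.9)/2) = 1.087. With equal p and equal r the shifts cancel and only precision is lost. Neither p nor r can be taken from the documents.

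**6. Exacerbation frequency.** SAP 9.3.5 defines an exacerbation by worsening symptoms plus escalation, which includes starting antibiotics or systemic steroids. SAP 5.6 lists oral steroid use, and an exacerbation evidenced by antibiotics near a CT, as exclusions. A subject can thus be removed for the event being counted.

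**The case against.** The strongest reply is that the four items are only examples. The governing test is potential to affect the primary efficacy analysis, applied at blinded review and documented separately, and that review could set endpoint-specific rules. This is fair, but the SAP does not say that it will. The general test does not separate the two co-primaries, and SAP 7.7 sends both to the same set.

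Second, little depends on the result. The primary analysis uses the FAS, the PPS is outside the testing hierarchy in SAP 7.4, and the co-primaries also have a supplementary estimand and an observed-cases analysis. That stands and limits the weight of the point. A joint set also mirrors the FAS, which requires data on both endpoints, but the FAS requirements concern baseline and early data, not events after Week 4.

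Third, the design should keep near-CT exacerbations few: Protocol section 6 requires 28 symptom-free days before the Week 24 scan, and exclusion criterion 18 protects the screening scan. That is correct for this criterion, but not for steroids or surgery.

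A reader might also infer several stronger things that the documents do not support:

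- *Anyone off drug for the whole CSNS week stays in the set.* On the literal non-use example this holds for gaps of 7 to 15 days covering Days 21–27 and for some gaps crossing a month boundary. A gap of 16 or more days within one month is excluded, and the blinded review may remove shorter ones.
- *A 30-day gap before the CT escapes by splitting 15/15 across two months.* This takes "one year = 365.25 days, and one month = 30.44 days", a unit-conversion rule, as the definition of a month in 5.6. The documents do not make that link.
- *84% of exclusions are irrelevant to CSNS.* The figure is a share of treatment days. Exclusions need not be evenly spread, and the CT criterion is tied to scan dates.
- *CSNS should ignore the exacerbation criterion.* An exacerbation after a run-in CT can disturb the baseline or Week 4 score.

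**Conclusion.** The point holds for the structure of the set. One undated PPS is applied to endpoints about 20 weeks apart (Day 27 against nominal Day 168), so steroid use, surgery or a Week 24 CT exacerbation after Day 27 removes a Week 4 score that was already final. Precision is lost to the extent that this happens. Bias arises if removal is related to the Week 4 change and differs by arm. Its size is unknown, and its direction rests on assumptions: the 8% to 12% attenuation above follows only from the rates and correlations chosen for illustration.

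The disagreement between SAP 5.6 and 7.7 over the key secondaries is plain on the text. If 5.6 governs, the exacerbation-frequency PPS analysis selects on its own outcome.

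The consequence is confined to sensitivity analyses. The FAS primary result and the type I error control are unaffected. This is a cheap improvement to make before unblinding, not a threat to the trial's conclusions.

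**What to change.** Before unblinding, amend SAP 5.6 and 7.7 as follows.

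1. **Week 4 CSNS (co-primary and pooled key secondary):** use only deviations dated through Day 27, including any exacerbation in the run-in or up to Day 27.
2. **APOV:** use deviations dated through the Week 24/ET CT.
3. **Exacerbation frequency:** if it is to have a PPS analysis, do not exclude subjects for an exacerbation or its treatment.
4. **Scope:** make 5.6 and 7.7 name the same endpoints.
5. **Non-use of drug:** count a gap as one continuous run whatever the month boundary. Judge it against Days 21–27 only where dosing dates exist. Protocol 5.7 describes visual inspection of returned units and SAP 8.1 a total dose count, so daily dosing dates may not be available.

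Stratification errors (SAP 4.4) are not dated events and can stay as an exclusion from every set.

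The cost is SAP wording and two or three flags instead of one, with no added subjects. Medication start and stop dates are already recorded (SAP 9.5.1). The drawback is that per-protocol populations will differ by endpoint, which the tables must label.

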6 STUDY POPULATION SUMMARY

All study population summaries will be based on the Safety Analysis Set, (reference Section 5.4), and summarized by treatment group and total population, unless otherwise indicated.

Descriptive statistics for continuous variables include n, mean, standard deviation (SD), standard error (SE) of the mean, median, minimum, and maximum. Descriptive statistics for categorical variables include subject counts and percentages. Percentages are based on the number of subjects in the analysis set for whom there are non-missing data at the specified visit, unless otherwise specified. Counts of “missing” will be presented if at least one treatment group has missing data.

6.1 Subject Disposition

The number of subjects in the Enrolled Set, Single-Blind Analysis Set, ITT Analysis Set, Safety Analysis Set, FAS, PPS will be summarized using descriptive statistics by treatment group and overall.

Subjects who completed the study, and subjects who discontinued the study prior to week 24, will be summarized by treatment group and overall, and reasons for study discontinuation will be summarized.

The denominator for calculating percentages in the Subject Disposition displays will be the ITT Analysis Set.

6.1.1 Subject Disposition with respect to Intercurrent Events

Subject disposition with respect to Intercurrent Events will be summarized for both the primary and supplemental estimands defined in Sections 7.1.3 and 7.2.1, respectively. The efficacy FAS population will be used for the Subject Disposition with respect to Intercurrent Events.

A subject listing of intercurrent events including subject outcomes under each estimand definition will be provided.

6.2 Demographics

The continuous variables of subject age, weight (kg), height (cm), and body mass index (BMI) (kg/m²), and the categorical variables of subject sex, ethnicity, and race will be summarized.

6.3 Subject Characteristics

The following subject characteristics will be summarized: nasal polyp status at baseline, prior sinus surgery status.

6.4 CRS History

Information pertaining to subjects’ chronic sinusitis history will be summarized.

6.5 Prior Medications

All prior medications will be coded using the World Health Organization dictionary of medical codes (WHO Drug, Version December 2018 or later). The incidence of prior medications will be summarized by therapeutic class and preferred term. Subjects are counted only once in each

therapeutic class category, and only once in each preferred term category. Prior medications will include all medications taken on or before the first dose of double-blind treatment. Further details on the definition of prior medications is provided in Section [9.5.1](#).

6.6 Medical History

A complete medical history will be obtained before randomization to ensure subjects qualify for the study. Medical, surgical and smoking history will be summarized.

6.7 Chronic Rhinosinusitis (CRS) Treatment History

Information pertaining to subjects' CRS treatment history will be summarized.

6.8 Nasal and Sinus Endoscopic Assessment

Results of the nasal and sinus endoscopic assessment performed during the placebo run-in period will be summarized.

6.9 Urine Drug Screening

Drug screen will be performed at the screening/placebo run-in period. Positive findings indicating drug abuse will lead to screen failure. Urine drug screen findings will be listed.

6.10 Protocol Deviations/Violations

Protocol violations and deviations considered to be major will be listed by treatment group. Reference Section [5.6](#) for definition of Per Protocol Analysis Set.

7 STATISTICAL METHODS FOR EFFICACY ANALYSES

Hypotheses testing and statistical inference for efficacy endpoints and the strategy for control of Type I error probability is described in Section 7.4. All statistical tests are 2-sided tests at the 5% level of significance. Statistical significance is defined as $p < 0.05$ (two-sided test). Nominal p-values will be provided for all other efficacy endpoints not included in the formal testing strategy.

